1.2.5.3. Safety Parameters

Safety evaluations will include assessment of adverse events (AEs) including serious AEs (SAEs) and IRRs, ECGs, vital signs (blood pressure, pulse rate, oral body temperature, and respiration rate), clinical laboratory tests (hematology, serum chemistry, thyroid function parameters, coagulation parameters, and urinalysis), and ophthalmology and physical examinations. Patients will be closely monitored for both acute and delayed IRRs. All IRRs will be recorded as AEs.

Mental status as it relates to suicidal ideation and behavior will be assessed using the Columbia–Suicide Severity Rating Scale (C-SSRS) questionnaire.

2. SUBJECT POPULATION

2.1. Population Definitions

The following subject populations (i.e., analysis sets) will be evaluated and used for presentation and analysis of the data:

- Full Analysis Set: All patients who were enrolled will be included in the full analysis set. The full analysis set will be the primary set for the analysis of PD data and clinical activity assessments.
- Safety Analysis Set: All patients in the full analysis set who received at least one dose of study drug. The safety analysis set will be used for the analysis of safety assessments.
- Pharmacokinetic (PK) Analysis Set: All patients in the Safety Analysis Set who have adequate PK data to determine at least one key PK parameter.

2.2. Protocol Deviations

A deviation is considered any departure from the procedures set forth in the protocol. Protocol deviations will be classified into major and minor by medical review prior to database lock. A major deviation is a deviation that may impact patient safety or efficacy interpretation (for example, failure to meet key inclusion and exclusion criteria, error in premedication or investigational product dosing with potential for safety implications). GCP deviations will be classified under major deviations as well. Deviations not designated as major will be considered minor.

All protocol deviations and major protocol deviations will be presented in separate data listings.

3. GENERAL STATISTICAL METHODS

3.1. Sample Size Justification

Based on the number of patients enrolled in Study ALN-TTR02-002, up to 28 patients are expected to be enrolled in this extension study. Of these patients, up to 19 are expected to be included in the PK/PD subgroup. Any patient with pre-existing cardiac amyloid involvement will be included in the Cardiac subgroup for analysis (see Section 3.7).

The sample size was chosen based on the study ALN-TTR02-002 enrollment and was not based on power calculations.

3.2. General Methods

All data listings that contain an evaluation date will contain a study day (Rel Day) relative to the first date of study medication, which is designated as Day 1. On-treatment study days will be calculated as evaluation date – first dose date +1 and pre-treatment days will be calculated as evaluation date – first dose date. For example, the day prior to study medication will be Day -1 and the second day after the first dose of study medication will be Day 2, etc.

Tabulations will be produced for appropriate demographic, baseline, clinical activity, PD, and safety parameters. For categorical variables, summary tabulations of the number and percentage of subjects within each category (with a category for missing data) of the parameter will be presented. For continuous variables, the number of subjects, mean, median, standard deviation (SD), minimum, and maximum values will be presented.

Laboratory data (including vitamin A and RBP) collected and recorded as below the limit of detection will be set equal to the lower limit of detection for the calculation of summary statistics.

As this is a Phase 2 extension study, formal statistical hypothesis testing will not be performed. Ninety-five percent confidence intervals (CIs) will be produced where indicated, and are intended to be descriptive in nature.

All data will be presented in by-subject data listings.

3.3. Computing Environment

All descriptive statistical analyses will be performed using SAS statistical software Version 9.3 or higher, unless otherwise noted. Medical history and AEs will be coded using the Medical Dictionary for Regulatory Activities (MedDRA) Version 16.0 (or later). Concomitant medications will be coded using the World Health Organization (WHO) Drug Dictionary Version Q12013 (or later).

3.4. Baseline Definitions

Unless otherwise noted, baseline will be defined as the study ALN-TTR02-003 Day 1 pre-dose value when non-missing, otherwise the latest value from amongst any screening or unscheduled assessments prior to dosing on Day 1 will be used (i.e., the measurement closest to and prior to dosing will be considered baseline). For PD parameters (TTR, RBP, vitamin A), baseline will be defined as the average of all records, including those from any unscheduled visits, prior to the date and time of first dose. For the mNIS+7/NIS+7 total score and individual components, grip test and 10m walk test, baseline is defined as the average of the Screening/Baseline assessments.

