Premedication Administration ^s			X	X	X	X	X	X	X	X	X		
Study Drug Administration ^t			X	X	X	X	X	X	X	X	X		
Plasma PK Sampling ^u			X ^v	X ^v	X ^v	X ^v	X				X	X ^w	
Urine PK Sampling ^x			X ^v	X ^v	X ^v	X ^v	X				X	X ^w	

Procedure	Visit Type	Screening/ Baseline ^a	Dosing										Mid- year/Annual Efficacy Assessment
			1 & 28	4 & 31	7 & 34	10 & 37	13 & 40	16 & 43	19 & 46	22 & 49	25 & 52	27 & 54	
	Study Week	NA											
	Study Day	Day -28 to -0	D0 & D189	D21 & D210	D42 & D231	D63 & D252	D84 & D273	D105 & D294	D126 & D315	D147 & D336	D168 & D357	D182 & D371	
	Window	NA	±3D ^b	±3D	±3D	±3D	±3D	±3D	±3D	±3D	±3D	±3D	±5D
PK/PD Subgroup Only													
TTR (ELISA and turbidimetric) ^y			X		X								
RBP and Vitamin A ^y			X		X								
Plasma PK Sampling			X ^z		X ^z								
Urine PK Sampling			X ^{aa}		X ^{aa}								
Cardiac Subgroup Only:													
Echocardiogram													X
Troponin I and NT-proBNP			X ^d					X				X	
Concomitant Medications		X						X					
Adverse Events								X ^{bb}					

Note: The schedule of assessments for patients administered ALN-TTR02 once every 4 weeks is provided in Appendix 2.

- a Assessments performed during the ALN-TTR02-002 study that occur within the Screening/Baseline timeframe will not need to be repeated at the Screening/Baseline visit.
- b Window does not apply to Day 0.
- c Any AEs from the previous study (ALN-TTR02-002) that are ongoing on Day 0 are to be recorded on the Medical History case report form for the current study (ALN-TTR02-003) and followed until resolution.
- d To be performed only on Day 0, not on Day 189.
- e On dosing days, weight will be measured predose.
- f On dosing days, vital signs will be measured predose. Vital signs to include: blood pressure, pulse rate, oral body temperature, and respiratory rate. Parameters are to be measured in the supine position using an automated instrument after the patient has rested comfortably for 10 minutes.
- g Triplicate recordings will be obtained.
- h A pregnancy test will be performed on all females of child-bearing potential at Screening/Baseline and any time pregnancy is suspected.
- i To be performed before administration of premedications and dosing with ALN-TTR02.

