5.5 Premedication Plan

Prior to ALN-TTR02, patients will receive the following premedications:

- Intravenous dexamethasone (10 mg) or equivalent, administered at least 60 minutes prior to the start of the infusion of ALN-TTR02;
- Oral paracetamol (500 mg) or equivalent at least 60 minutes prior to the start of the infusion of ALN-TTR02;
- Intravenous H2 blocker (e.g., ranitidine 50 mg, famotidine 20 mg, or equivalent other H2 blocker dose) at least 60 minutes prior to the start of the infusion of ALN-TTR02; and
- Intravenous H1 blocker: diphenhydramine 50 mg (or equivalent other IV H1 blocker available at the study site) at least 60 minutes prior to the start of the infusion of ALN-TTR02. Hydroxyzine or fexofenadine 25 mg PO or cetirizine 10 mg PO may be substituted for any patient who does not tolerate IV diphenhydramine or other IV H1 blocker.

Patients will be started on the above premedication regimen. However, modifications may be made to the premedication regimen after consultation with the medical monitor either due to a patient's inability to tolerate one or more of the premedications or to the occurrence of IRRs unresponsive to slowing of the infusion rate.

- If a patient is having difficulty tolerating the steroid premedication regimen (e.g., patient develops uncontrolled hyperglycemia, altered mental status, or other complication), then lowering of the steroid premedication may be allowed for that patient after consultation with the medical monitor.
- If after consultation with the medical monitor, it is agreed that an individual patient's steroid premedication will be lowered, then the following steps **must be followed**:
 - 1) If the current steroid dosage is 10 mg intravenous dexamethasone or equivalent, then the patient may be lowered in increments no greater than 2.5 mg intravenous dexamethasone or equivalent.
 - 2) After each incremental lowering below 10 mg intravenous dexamethasone or equivalent, the patient must receive three consecutive intravenous doses of patisiran without IRR and continued signs or symptoms of steroid intolerance before further reductions in steroid premedications.
 - 3) The premedication steroid dosage should not be reduced below 5 mg intravenous dexamethasone or equivalent.

Alternatively, if a patient experiences an IRR when 10 mg or less of intravenous dexamethasone or equivalent is used as the steroid premedication, then proceed to Section 5.11.

Further details can be found in the Study Reference Manual.

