Urine PK Sampling ^x		X ^v	X ^v	X ^v	X ^v	X ^v	X					X	X ^w

Procedure	Visit Type	Screening/ Baseline ^a	Dosing										Mid- year/Annual Efficacy Assessment
			1 & 28	4 & 31	7 & 34	10 & 37	13 & 40	16 & 43	19 & 46	22 & 49	25 & 52	27 & 54	
	Study Day	Day -28 to -0	D0 & D189	D21 & D210	D42 & D231	D63 & D252	D84 & D273	D105 & D294	D126 & D315	D147 & D336	D168 & D357	D182 & D371	
	Window	NA	±3D ^b	±3D	±3D	±3D	±3D	±3D	±3D	±3D	±3D	±5D	
PK/PD Subgroup Only													
TTR (ELISA and turbidimetric) ^y													
RBP and Vitamin A ^y													
Plasma PK Sampling													
Urine PK Sampling													
Cardiac Subgroup Only:													
Echocardiogram													
Troponin I and NT-proBNP													
Concomitant Medications													
Adverse Events													

Note: The schedule of assessments for patients administered ALN-TTR02 once every 4 weeks is provided in Appendix 2.

- a Assessments performed during the ALN-TTR02-002 study that occur within the Screening/Baseline timeframe will not need to be repeated at the Screening/Baseline visit.
- b Window does not apply to Day 0.
- c Any AEs from the previous study (ALN-TTR02-002) that are ongoing on Day 0 are to be recorded on the Medical History case report form for the current study (ALN-TTR02-003) and followed until resolution.
- d To be performed only on Day 0, not on Day 189.
- e On dosing days, weight will be measured predose.
- f On dosing days, vital signs will be measured predose. Vital signs to include: blood pressure, pulse rate, oral body temperature, and respiratory rate. Parameters are to be measured in the supine position using an automated instrument after the patient has rested comfortably for 10 minutes.
- g Triplicate recordings will be obtained.
- h A pregnancy test will be performed on all females of child-bearing potential at Screening/Baseline and any time pregnancy is suspected.
- i To be performed before dosing with ALN-TTR02.

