4.6. Safety Analyses

Safety analyses will be conducted using the Safety Analysis Set. Baseline values for all safety analyses will be defined as the last observation prior to dosing.

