4.6.6. Premedication

All patients received premedication in order to reduce the potential of an IRR. The original premedication regimen as outlined below was used at the start of the study. A subset of patients experienced AEs suspected to be related to steroids (eg, flushing) and were transitioned to a modified premedication regimen, with a reduced dose of corticosteroid to mitigate these events, as sanctioned in the protocol. After observing that the subset of patients tolerated the lower corticosteroid dose with no increase in IRRs, the protocol was amended (Global Amendment 1) to transition the rest of the patients to the modified premedication regimen (see below).

The following original premedication regimen was used prior to Global Amendment 1:

- Dexamethasone 8 mg PO or equivalent administered the evening before dosing and 20 mg PO at least 60 minutes prior to the start of the infusion of patisiran;
- Paracetamol 500 mg PO or equivalent administered the evening before dosing and at least 60 minutes prior to the start of the infusion of patisiran;
- H2 blocker PO (e.g., ranitidine 150 mg or famotidine 20 mg or equivalent other H2 blocker dose) administered the evening before dosing and at least 60 minutes prior to start of the infusion of patisiran; and
- H1 blocker PO, 10 mg cetirizine or equivalent (hydroxyzine 25 mg or fexofenadine could be substituted if patient did not tolerate cetirizine) administered the evening before dosing and at least 60 minutes prior to start of the infusion of patisiran.

The following modified premedication regimen was instituted with Global Amendment 1:

- Dexamethasone 10 mg IV or equivalent, administered at least 60 minutes prior to the start of the infusion of patisiran;
- Paracetamol 500 mg PO or equivalent at least 60 minutes prior to the start of the infusion of patisiran;
- H2 blocker IV (e.g., ranitidine 50 mg, famotidine 20 mg, or equivalent other H2 blocker dose) at least 60 minutes prior to the start of the infusion of patisiran; and
- H1 blocker IV, diphenhydramine 50 mg (or equivalent other IV H1 blocker available at the study site) at least 60 minutes prior to the start of the infusion of patisiran. Hydroxyzine

25 mg PO or fexofenadine 30 or 60 mg PO or cetirizine 10 mg PO could be substituted for any patient who did not tolerate IV diphenhydramine or other IV H1 blocker.

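### For patients first dosed under the original premedication regimen, the laboratory baseline follows an evening steroid dose, and the laboratory summaries are not split by regimen

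*SAP*

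**What the plan says.** **Baseline.** The general rule in SAP 3.4 is that "baseline will be defined as the study ALN-TTR02-003 Day 1 pre-dose value when non-missing"; otherwise the latest earlier value is used. SAP 4.6 adds: "Baseline values for all safety analyses will be defined as the last observation prior to dosing". SAP 3.4 has separate rules for the pharmacodynamic parameters and the neuropathy and motor tests, but none for laboratory tests.

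**Premedication.** SAP 4.6.6 says: "The original premedication regimen as outlined below was used at the start of the study". Its steroid component, timed against the infusion, was: "Dexamethasone 8 mg PO or equivalent administered the evening before dosing and 20 mg PO at least 60 minutes prior to the start". A subset of patients moved to a modified regimen, and Global Amendment 1 then moved the rest. The modified regimen gives 10 mg IV dexamethasone on the dosing day and nothing the evening before.

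**Laboratory analysis.** SAP 4.6.3 plans actual values, change and percentage change from baseline by visit. It also plans low/normal/high shift tables for every continuous parameter. The by-regimen summaries in SAP 4.6.6 cover TTR reduction and AE/IRR incidence only.

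**Draw timing.** Protocol Table 1-1, footnote i, on the laboratory rows: "To be performed before administration of premedications and dosing with ALN-TTR02". Protocol 7.2.5 says the same. The SAP's copy of footnote i reads: "To be performed before dosing with ALN-TTR02". Footnote e of Table 1-2 differs between the two documents in the same way.

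**The concern.** Safety is the primary objective, and the steroid is given with every infusion. Protocol 5.5 accepts that it can affect a laboratory value, since one example of steroid intolerance is that the "patient develops uncontrolled hyperglycemia"; glucose is in the chemistry panel.

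If the baseline sample follows an evening steroid dose and later samples do not, part of the reported change reflects the premedication switch and not the study drug. Regimen and time on study are also entangled, because patients move from one regimen to the other as the study proceeds. A by-visit laboratory table that ignores regimen cannot separate the two. In the shift tables, a patient whose baseline value is pushed above the upper limit starts in the high row and cannot record a normal-to-high shift.

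**Working it through.** The documents give no figure to reproduce, so the check is algebra on change from baseline.

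**Notation.** For one patient and one test, let B be the baseline value without a recent steroid dose, P the post-baseline value without one, and s the residual effect of the evening-before dose at the next pre-dose draw. I assume that s is additive and stable within a patient.

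**Where the samples fall.** Protocol 6.2.1.1 puts on-treatment chemistry (every 3 months) and hematology (every 6 months) pre-dose on dosing days. The mid-year and annual visit list in Protocol 6.2.2 contains neither. By the prose, the scheduled post-baseline draws away from dosing are the 21-day follow-up (6.2.5.1) and Early Termination (6.3). I rely on the prose because the columns of the schedule tables are not reliably readable in the text I have.

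**Day 1 baseline, patient who started on the original regimen (baseline = B + s):**

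| Draw | Observed value | Change from baseline |
|---|---|---|
| Dosing day, original regimen | P + s | (P + s) − (B + s) = P − B |
| Dosing day after the switch, drawn before premedication | P | P − (B + s) = (P − B) − s |
| 21-day follow-up or Early Termination | P | (P − B) − s |

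A patient first dosed under the modified regimen and sampled before premedication has baseline B, so change is P − B and the issue does not arise.

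**Percentage change.** On original-regimen dosing days the numerator is clean, but the denominator is B + s instead of B.

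**Screening baseline, same patient, if Screening is free of steroid (baseline = B):**

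| Draw | Change from baseline |
|---|---|
| Dosing day, original regimen | (P + s) − B = (P − B) + s |
| Dosing day after the switch, or 21-day follow-up | P − B |

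Neither baseline is clean across a switch; each moves the term s to different visits. Where both values exist, their difference is (B + s) − B = s plus ordinary within-patient variation, so the trial's own data can indicate how large s is.

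**Shift tables.** The category depends on B + s against the normal limits, not on a difference, so the cancellation in the first table does not carry over. If B is normal and B + s exceeds the upper limit, the patient is high at baseline for every later comparison.

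**What cannot be filled in.** The documents do not give s, the number of patients first dosed under the original regimen (SAP 3.1 puts total enrolment at up to 28) or the switch dates.

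**The case against.** The strongest defence has four parts.

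- **The closest pre-dose value is a conventional baseline and suits the original-regimen visits.** This stands. On those days the steroid term cancels, while a Screening baseline would show a premedication effect as an on-treatment change. A reader might infer that Screening should replace Day 1 as the primary baseline; the algebra does not support that. Screening is also not shown to be steroid-free. Protocol Table 1-1, footnote a, lets assessments from ALN-TTR02-002 serve as Screening, and Protocol 1.6.2.1 says that a similar premedication regimen was used in earlier ALN-TTR02 studies.
- **The protocol governs sampling.** This largely stands. From the SAP footnote a reader might infer that Day 1 samples also followed the 20 mg dose on the dosing day. The protocol requires the draw before premedications, and the SAP presents its tables as the protocol's schedule. The protocol version in force under the original regimen is not available, so its draw rule cannot be checked. A rule about same-day timing would in any case not remove the evening dose.
- **Other outputs do not depend on baseline.** SAP 4.6.3 also plans actual values by visit, tables of potentially clinically significant abnormalities and listings of out-of-range results. AEs are split by regimen. New abnormalities would therefore not vanish from the report. What remains exposed is the change-from-baseline and shift summaries.
- **The study is descriptive.** There is no hypothesis testing (SAP 3.2), so no formal conclusion turns on this. That also stands and limits the severity.

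Two further inferences go beyond the documents. One is an effect on neutrophils, which they do not mention. The other is a numerical share of patients high at baseline. With an assumed glucose mean of 5.2, SD 0.5 and upper limit 6.0 mmol/L, that share is 5%, 27%, 66% or 99% for an assumed s of 0, 0.5, 1.0 or 2.0 mmol/L. These figures only restate the assumed shift; no input comes from the documents.

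**Conclusion.** The concern holds in a limited form. It applies to patients whose first dose in this study was under the original regimen and who have a Day 1 laboratory value. For them, change from baseline is like for like until the switch. It is then shifted by −s on modified-regimen dosing days, and also at the 21-day follow-up and any other draw with no evening-before dose. The baseline category in the shift tables may be affected throughout.

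The size cannot be stated, for want of the three quantities named above. Hyperglycemia is the only laboratory-related steroid effect that the documents name, so glucose is the one test for which they support the concern directly; any other test is an assumption. The direction assumes that s is additive and stable within a patient and that post-switch samples were drawn before premedication.

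This is a minor point. The planned baseline is defensible. The gap is that the laboratory summaries do not use the regimen split that SAP 4.6.6 already plans for other outcomes.

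**What to change.** 1. Keep the Day 1 pre-dose value as the primary laboratory baseline.
2. In SAP 4.6.3, extend the by-regimen split of SAP 4.6.6 to by-visit laboratory changes and shift tables, at least for glucose. For the shift tables, take the post-baseline category separately within each regimen period.
3. Add a sensitivity analysis whose baseline is the last value before the first premedication dose of this study. First check that Screening values carried over from ALN-TTR02-002 are clear of that study's premedication, and flag or exclude any that are not.
4. Reconcile footnote i of SAP Table 1-1 and footnote e of SAP Table 1-2 with the protocol's rule that laboratory samples precede premedications.

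The cost is SAP wording, one extra baseline derivation and a few more tables. With at most 28 patients, some cells will be small, and the sensitivity baseline can be up to 28 days older than Day 1. No new data collection is needed.

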1.3 Summary of Clinical Data with ALN-TTR02

A Phase 1 multicenter, randomized, placebo-controlled, single-blind, single-ascending dose clinical study of ALN-TTR02 in healthy volunteers was completed in the UK. ALN-TTR02 was administered as a single 60-minute IV infusion to healthy volunteers across doses of 10 to 500 µg/kg. Patients were premedicated with dexamethasone, H1 and H2 blockers, and paracetamol prior to dosing to minimize the risk of infusion-related reactions (IRRs). Significant pharmacology in terms of TTR protein lowering (>80% reduction from pretreatment baseline) was observed at doses \geq 0.15 mg/kg. Transthyretin levels showed evidence of recovery beginning at around Day 21-28, with return to baseline by Day 70.

An open-label Phase 2 multiple ascending dose study of ALN-TTR02 in ATTR patients with FAP (Study ALN-TTR02-002) is currently enrolling patients to determine the safety and tolerability, pharmacokinetic (PK), and pharmacodynamic (PD) of a 60-70 minute IV infusion of ALN-TTR02 administered once every 3 -4 weeks for 2 doses. There have been no discontinuations or dose-limiting toxicities, and dosing is currently ongoing with the 0.3 mg/kg ALN-TTR02 dose. The preliminary PD effects on TTR are consistent with the data observed in the Phase 1 ALN-TTR02-001 study. It is anticipated that the

ALN-TTR02 dose and regimen for long-term dosing will be determined based on Study ALN-TTR02-002.

Further details on these studies can be found in the ALN-TTR02 IB.

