4.2 Inclusion Criteria

Each patient must meet all of the following criteria within the Screening/Baseline period to be enrolled in the study:

1. Patients have previously received and tolerated ALN-TTR02 in Study ALN-TTR02-002.
2. Karnofsky performance status of 60% or greater.
3. Absolute neutrophil count (ANC) ≥ 1500 cells/mm³, platelet count $\geq 100,000$ cells/mm³, and hemoglobin ≥ 10 g/dL.
4. Adequate liver function, demonstrated by an aspartate transaminase (AST) and alanine transaminase (ALT) levels $\leq 2.5 \times$ the upper limit of normal (ULN), total bilirubin level within normal limits, albumin >3 g/dL, international normalized ratio (INR) ≤ 1.2 .
5. Adequate renal function, demonstrated by serum creatinine level $\leq 1.5 \times$ ULN.
6. Women of child-bearing potential must have a negative pregnancy test, cannot be breast feeding, and must be using 2 highly effective methods of contraception prior to screening, throughout study participation, and for 75 days after the last dose of study medication. Highly effective methods of birth control are defined as: hormonal - oral, implantable, injectable, or transdermal contraceptives in conjunction with spermicide, condom, or diaphragm; mechanical - spermicide in conjunction with a barrier such as a condom or diaphragm; intrauterine device in conjunction with spermicide or condom; or surgical sterilization of partner in conjunction with spermicide, condom, or diaphragm.
7. Males agree to use appropriate contraception throughout study participation and for 75 days after the last dose of study medication.
8. Patient is willing and able to comply with protocol-required visit schedule and visit requirements and provide written informed consent.

Additional inclusion criteria for patients participating in the PK/PD subgroup include:

9. At the time of enrollment, at least 6 months have elapsed since the patient's last dose of ALN-TTR02.

Additional inclusion criteria for patients participating in the Cardiac subgroup:

10. Have a left ventricular wall thickness of ≥ 13 mm on transthoracic echocardiogram.

11. Be normotensive or have hypertension that is well-controlled.
12. Absence of aortic valve disease.

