4.3 Exclusion Criteria

Patients meeting any of the following criteria within the Screening/Baseline period (Day -28 to Day 0) will be excluded from the study:

1. Patient is pregnant or nursing.
2. Patient has had a liver transplant.
3. Has a known or suspected systemic bacterial, viral, parasitic, or fungal infection.
4. Patient received an investigational agent, other than tafamidis or diflunisal, within 30 days prior to first dose study drug administration.
5. Patient has a New York Heart Association heart failure classification >2 (see Appendix 3).
6. Patient has unstable angina.
7. Patient has uncontrolled clinically significant cardiac arrhythmia.
8. Patient is considered unfit for the study by the Principal Investigator (PI).

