9 STATISTICAL METHODS

9.1 Sample Size

Based on the number of patients expected to be enrolled in Study ALN-TTR02-002, up to 28 patients are expected to be enrolled in this extension study. Of these patients, up to 25 are expected to be included in the PK/PD subgroup. Any patient with pre-existing cardiac amyloid involvement will be included in the Cardiac subgroup.

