3.7. Subpopulations

Patients who have pre-existing cardiac amyloid involvement will be eligible for inclusion in the cardiac subgroup for analysis. The inclusion criteria are the following:

- 1) Have a left ventricular wall thickness of ≥ 13 mm on transthoracic echocardiogram;
- 2) Be normotensive or have hypertension that is well-controlled;
- 3) No aortic valve disease.

Patients enrolled in the cardiac subgroup will complete additional clinical activity assessments to evaluate cardiac structure/function. This will be achieved through echocardiograms and monitoring of NT-proBNP and troponin I.

Patients will be eligible for inclusion in the PK/PD subgroup if their last dose of patisiran was administered at least 6 months prior to the first dose in this study. Patients enrolled in the PK/PD subgroup will have additional samples taken for evaluation of PK and PD (TTR and secondary PD biomarkers [RBP and vitamin A]).

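### The TTR, RBP and vitamin A baseline carries no condition on time since the last Study 002 dose, so a patient entering within about 70 days could have a suppressed baseline and an understated percentage reduction

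*SAP*

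**What the plan says.** SAP 3.4 departs from its general last-value rule for the pharmacodynamic markers: "For PD parameters (TTR, RBP, vitamin A), baseline will be defined as the average of all records, including those from any unscheduled visits", before the date and time of first dose. No minimum interval from earlier exposure is attached, and the records are not expressly limited to this study. SAP 4.3 analyses PD in the Full Analysis Set, which is everyone enrolled. It reports change and percentage change from baseline, maximum and mean TTR reduction, and serial TTR by genotype, stabilizer use, gender and age. SAP 4.6.6 adds TTR reduction by premedication regimen.

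Every patient has already been dosed. Protocol 1.3 describes Study 002 as dosing "administered once every 3 -4 weeks for 2 doses". From the Phase 1 study it reports: "Transthyretin levels showed evidence of recovery beginning at around Day 21-28, with return to baseline by Day 70".

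Two rules bear on the gap between studies:
- PK/PD subgroup only (SAP 3.7; Protocol 4.2, criterion 9): patients qualify "if their last dose of patisiran was administered at least 6 months prior to the first dose in this study".
- All patients (Protocol 4.3, criterion 4), as an exclusion: "Patient received an investigational agent, other than tafamidis or diflunisal, within 30 days prior to first dose study drug administration".

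On subgroup size, Protocol 9.1 says "up to 25 are expected to be included in the PK/PD subgroup", out of up to 28 patients. SAP 3.1 lowers the 25 to 19.

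**The concern.** The TTR effect is the first secondary objective in both documents, and percentage reduction is how it will mostly be read. If TTR is still suppressed when baseline is taken, the denominator is too small and the reduction is understated. Patients with a recovered baseline and patients with a suppressed one would then be averaged together. The effect on the overall mean may be modest. In the small strata of SAP 4.3 and 4.6.6, one or two short-gap patients could create an apparent difference between genotypes, stabilizer users or premedication regimens that reflects only time since the last dose.

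**Working it through.** The plan gives no figure to reproduce: SAP 3.1 says the sample size was not power-based, and the study is descriptive. The check is whether a suppressed baseline is permitted, and how large the effect would be.

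**Is it permitted?** The universal floor is 30 days, and only if ALN-TTR02 itself counts as an investigational agent, which is the literal reading. Recovery is complete by Day 70. Outside the PK/PD subgroup, a gap of 30 to 70 days is therefore eligible and falls within the recovery period.

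**Inputs.** True reduction from the untreated level R = 80% (Protocol 1.5 and 1.6.1 give about this figure at 0.3 mg/kg). Recovery starts at Day 21 or Day 28 and ends at Day 70 (Protocol 1.3). Assumptions not in the documents: residual suppression is 80% when recovery starts and then falls in a straight line to zero.

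**Formulas.** With gap d in days and recovery starting at Day 21, residual suppression s = 0.80 × (70 − d)/49. With a Day 28 start the divisor is 42. Reported reduction = 1 − (1 − R)/(1 − s) = 1 − 0.20/(1 − s).

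Example at d = 40, Day 21 start: s = 0.80 × 30/49 = 0.490, so the reported reduction is 1 − 0.20/0.510 = 0.608.

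| Gap (days) | s, Day 21 start | Reads | s, Day 28 start | Reads |
|---|---|---|---|---|
| 30 | 65% | 42% | 76% | 16% |
| 40 | 49% | 61% | 57% | 53% |
| 50 | 33% | 70% | 38% | 68% |
| 60 | 16% | 76% | 19% | 75% |
| 70 or more | 0% | 80% | 0% | 80% |

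These use Day 0 records only.

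**Averaging in a screening record.** Table 1-1 schedules one TTR sample at screening (Day -28 to 0) and two on Day 0. Take a 70-day gap with screening at Day -28, which is 42 days after the dose. With a Day 21 start, s at screening = 0.80 × 28/49 = 0.457, the average s = (0.457 + 0 + 0)/3 = 0.152, and the reduction reads 76.4% instead of 80%. Some exposure can therefore reach a gap of 70 + 28 = 98 days.

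**Mean over 28 patients**, with k patients at a 40-day gap (Day 21 start) and the rest recovered: [(28 − k) × 80 + k × 60.8]/28.
- k = 0: 80.0%
- k = 3: (2000 + 182.4)/28 = 77.9%
- k = 9: (1520 + 547.2)/28 = 73.8%

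The values 3 and 9 are 28 − 25 and 28 − 19. They count patients outside the stated subgroup ceilings if 28 enroll, and serve only as illustrations.

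**RBP and vitamin A.** The documents give no recovery timing for these, so the size of any bias cannot be computed.

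**The case against.** The strongest reply is that nobody may be affected. The subgroup sizes are ceilings; being outside the subgroup does not show a gap under 6 months, still less under 70 days. Protocol 1.6.1 reports mean knockdown of about 80% over about 16 months, which argues against heavy contamination, although its baseline is not stated. The recovery timing comes from single doses in healthy volunteers, and Study 002 was an ascending-dose study, so 80% residual suppression will not hold for everyone. Observed TTR levels are also tabulated, plotted by patient and listed, so a low baseline would be visible. All of this stands, and it limits the size of the point. It does not remove the gap in the definition.

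A second reply is that the protocol provides for an additional PD baseline analysis (synopsis, 3.4, 7.5.1, 9.2.5, 9.2.8). In each place it is optional. The SAP does not carry it over, and the separate PK and PK/PD analysis plan is not available here. It is not a commitment.

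Three stronger readings are tempting and should be resisted:
- A reader might infer that the TTR-mNIS+7 correlation in SAP 4.4.1 is biased too. Its predictor is the value 17 days after the first dose, a sample scheduled only in the PK/PD subgroup (Protocol 7.3.1; Table 1-1, footnote y), whose gap is at least 6 months.
- A reader might infer that the recovery follow-up is distorted by SAP 3.4. That rule is set in Protocol 6.2.5.2 and 6.4 against Screening/Baseline visit levels, and changing the SAP definition would not alter it.
- A reader might take Table 1-1, footnote a, as evidence of close roll-over: "Assessments performed during the ALN-TTR02-002 study that occur within the Screening/Baseline timeframe will not need to be repeated at the Screening/Baseline visit". It concerns assessments, not doses, and a late Study 002 follow-up visit would fit it equally well.

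**Conclusion.** The point holds as a gap in the baseline definition. SAP 3.4 permits a suppressed TTR baseline for patients outside the PK/PD subgroup who have any baseline record within about 70 days of their last Study 002 dose. The direction is certain: the percentage reduction is understated. The size is not. For an affected patient, a true 80% would read about 42% to 76% at gaps of 30 to 60 days, under linear recovery from Day 21; a Day 28 start gives lower readings. For the cohort, the mean is 80% if no one is affected and 73.8% in the illustration with 9 patients at 40 days. These figures rest on the assumed recovery shape, healthy-volunteer timing and unknown gaps. Because any bias runs against the drug and the study is descriptive, this is a cheap improvement; the documents do not show that the TTR results are unsound.

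**What to change.** Keep the SAP 3.4 baseline for the main tables and add three things:

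1. State in SAP 3.4 that the averaged records exclude on-treatment Study 002 records.
2. Report the distribution of time from the last Study 002 dose to the first dose in this study. If no baseline record falls within about 70 days, this alone settles the matter.
3. Add a sensitivity table of percentage change in TTR, RBP and vitamin A that (a) uses the Study 002 pre-first-dose value as baseline for patients with any baseline record within about 70 days of their last Study 002 dose, and (b) is restricted to patients at least 6 months from that dose.

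Replacing the main baseline for everyone under 6 months would go too far: recovery is cited as complete by Day 70, so sound baselines would be discarded.

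The cost is SAP wording, a merge with parent-study data the sponsor should already hold, and one extra table. No new patient procedures are needed. The downside is a second baseline source, possibly from different assay runs, which is why it belongs in a sensitivity analysis.
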